1.1.2 Initial Treatment for Non–Muscle-Invasive Bladder Cancer

The backbone of therapy for patients with NMIBC is surgical resection with TURBT. This procedure is both diagnostic and therapeutic, with the goal of complete removal of malignant tumor and histologic review of resected disease to determine the risk of recurrence. One pitfall of this procedure is that it is operator-dependent. Brausi et al. (2002) demonstrated that the quality of TURBT had a major impact on recurrence rates. In a study of 83 patients with NMIBC, Grimm et al. (2003) observed that residual disease was found in 27% of Ta and 53% of T1 cases.

Divrik et al. (2010) demonstrated the benefit of repeat TURBT in a prospective, randomized study. Data from this study showed 5-year recurrence-free survival (RFS) rates of 59% with re-TURBT, compared with 32% with single TURBT alone. Similarly, the 5-year progression-free survival (PFS) rates were 93% with re-TURBT, compared with 79% for the single TURBT alone (Divrik et al. 2010). As a result, repeat or restaging TURBT is routinely recommended, especially for cases of an incomplete initial TURBT, absence of muscle layer in the resected specimen (with the exception of Ta low-grade tumors and primary CIS), all T1, and all high-grade tumors (except CIS) (Babjuk et al. 2011).

Use of radical cystectomy, a treatment option for high-risk NMIBC, can be curative but remains controversial for most patients (Skinner 2007). Data from a study by Denzinger et al. (2007), evaluating early cystectomy as a treatment option for high-risk NMIBC, revealed a 30% incidence of upstaging following cystectomy. Cancer-specific survival rates were prolonged in the early cystectomy group compared with the late cystectomy group; the presence of CIS was a major determining factor for outcome (Denzinger et al. 2007). The EAU recommends considering cystectomy as an initial treatment option for the subgroup of patients with VHR NMIBC defined in the previous section (Babjuk et al. 2013).

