- If cytology results are Suspicious or Indeterminate and the biopsies are negative, then treat as if the result was negative
- All occurrences of positive urine cytology will require further evaluation by cystoscopy and/or upper tract imaging. A positive cytology result only indicates presence of disease and cannot be used alone to determine disease progression.

The date of a positive cytology result can be used for the date of recurrence, if the results of the cystoscopy, biopsy, or upper urinary tract assessment shows recurrence.

Patients with persistent and/or recurrent high grade NMIBC without progression (stage or grade progression of active disease, or the presence of new disease) at 12 weeks from treatment initiation may continue on study treatment.

Patients with recurrent low-grade papillary disease will be required to undergo resection with TURBT (unless medically contraindicated) and may continue on study and receive study treatment.

Indications for Discontinuation from Study for Disease Progression

- Stage or grade progression at any timepoint would require discontinuation from study therapy.
- Patients with persistent and/or recurrent high-grade NMIBC (any pT1, high grade pTa, or CIS) on or after the 6-month biopsy will be discontinued from study treatment and offered the option to undergo cystectomy or other bladder-sparing modalities as is clinically appropriate. Patients who undergo cystectomy will be requested to submit additional tissue from their cystectomy specimens.
- Patients with evidence of disease progression to muscle-invasive or metastatic disease at any timepoint will be discontinued from study treatment.

For all patients, additional evaluation (imaging, exam under anesthesia, biopsies) should be performed at investigator discretion for any of the following circumstances:

- Abnormal cystoscopy
- Positive urine cytology
- Two sequential suspicious or indeterminate urine cytology specimens

Study treatment with atezolizumab may be continued for a maximum of 32 q3w cycles or a total of 96 weeks of therapy. BCG treatment (induction and maintenance) may be continued for a maximum of 120 weeks (as clinically indicated; see [Appendix 3](#)). All study treatment will be discontinued in patients who undergo cystectomy or experience disease recurrence/progression or unacceptable toxicity, and in those who are not benefiting from study treatment (in the opinion of the investigator or the patient).

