3.5.4 Efficacy Outcome Measures

The primary efficacy outcome measure for this study is as follows:

- CR at the 6-month evaluations after the start of study treatment. Patients must be evaluated for CR by both cystoscopy and cytology and bladder biopsies will be required for the 6-month CR disease assessment.

The secondary efficacy outcome measures for this study are as follows:

- CR at the 3-month disease assessment, evaluated by both cystoscopy and cytology.
- Duration of CR, defined as time from first occurrence of a documented CR until the time of recurrence of NMIBC or death from any cause
- RFS rate at 6, 12, and 18 months, defined as the proportion of patients who are alive and free of persistent/recurrent high-risk NMIBC
- Bladder-intact DFS, defined as time from first study treatment to earliest evidence of progression to muscle-invasive disease in the bladder, regional pelvic progression, distant metastasis, bladder cancer–related death, or cystectomy or death from any cause
- PFS, defined as the time from first study treatment to the first occurrence of progression to muscle-invasive disease or death from any cause
- CFS, defined as the time from first study treatment to cystectomy or death from any cause
- Overall survival, defined as the time from first study treatment to death from any cause

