At the investigator's discretion, cystoscopy and/or urine cytology may be repeated at any time if progressive or recurrent disease is suspected.

At the 6 month timepoint (24 week visit), documentation of a complete response (CR) is required to continue on study treatment.

Definition of Complete Response (must meet all 3 criteria):

- Cytology: not positive (see below)
- Upper Urinary Tract Imaging (if performed): normal, or abnormal but supportive of CR (with non-positive selective ureteral cytologies)
- Cystoscopy: bladder appears normal; or bladder appears abnormal but all biopsies are negative; or any grade papilloma, any grade PUNLMP, or low grade pTa

Interpretation of Urine Cytology:

- If results are Unsatisfactory, Atypical Cell, Suspicious, or Indeterminate, then assay must be repeated no less than 24 hours and up to 21 days later
- If the results are again Unsatisfactory or Atypical Cell (2 in a row), then treat as if the result was negative
- Two consecutive Suspicious or Indeterminate urine cytology specimens require further evaluation by cystoscopy and/or upper tract imaging as deemed appropriate by the investigator
- If cytology results are Suspicious or Indeterminate and the biopsies are negative, then treat as if the result was negative
- All occurrences of positive urine cytology will require further evaluation by cystoscopy and/or upper tract imaging. A positive cytology result only indicates presence of disease and cannot be used alone to determine disease progression.

The date of a positive cytology result can be used for the date of recurrence, if the results of the cystoscopy, biopsy, or upper urinary tract assessment shows recurrence.

Patients with persistent and/or recurrent high grade NMIBC without progression (stage or grade progression of active disease, or presence of new disease) at 12 weeks from treatment initiation may continue on study treatment. to muscle-invasive disease.

Patients with recurrent low-grade papillary disease will be required to undergo resection with TURBT (unless medically contraindicated) and may continue on study and receive study treatment.

Indications for Discontinuation from Study Treatment for Disease Progression

- Stage or grade progression at any timepoint would require discontinuation from study therapy.

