- Patients with persistent and/or recurrent high-grade NMIBC (any pT1, high grade pTa, or CIS) on or after the 6-month biopsy will be discontinued from study treatment and offered the option to undergo cystectomy or other bladder-sparing modalities as is clinically appropriate. Patients who undergo cystectomy will be requested to submit additional tissue from their cystectomy specimens.
- Patients with evidence of disease progression to muscle-invasive or metastatic disease at any timepoint will be discontinued from study treatment.

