4.6.2 Study Treatment Discontinuation

Patients must discontinue study treatment if they experience any of the following:

- Persistence/recurrence of disease with high grade lesion (any pT1, high-grade Ta, or CIS) detected any time on or after the 6-month bladder biopsy.
 - Patients with persistent and/or recurrent high-grade NMIBC without progression at 12 weeks may continue in the study, provided there is no evidence of progression to muscle-invasive disease.
- Disease progression (e.g., muscle-invasive or metastatic UC)
- Symptomatic deterioration (i.e., uncontrollable pain secondary to disease or unmanageable ascites, etc.) attributed to disease progression as determined by the investigator after integrated assessment of radiographic data, biopsy results, and clinical status.
- Intolerable toxicity related to atezolizumab or the combination of BCG and atezolizumab, including development of an immune-mediated adverse event determined by the investigator to be unacceptable given the individual patient's potential response to therapy and severity of the event
- Any medical condition that may jeopardize the patient's safety if he or she continues on study treatment
- Use of another non-protocol anti-cancer therapy (see Section [4.4.2](#))
- Pregnancy

The primary reason for study treatment discontinuation must be documented in the eCRF.

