6.4.2 Secondary Efficacy Endpoints

All assessments will be based on investigator assessments of tumor response/recurrence/progression and cause of death. The secondary efficacy endpoints for this study are as follows.

- CR at the 3-month disease assessment, evaluated by both cystoscopy and cytology.
- Duration of CR will be defined for patients with a CR as the time from the first occurrence of a documented complete response to recurrence of high-grade NMIBC or death from any cause. Data for patients without an event will be censored at the last date known to be alive and recurrence free.
- RFS rate at 6, 12, and 18 months, defined as the proportion of patients who are alive and free of persistent/recurrent high-grade NMIBC. Data for patients without an event will be censored at the last date known to be alive and free of persistent/recurrent NMIBC.
- Bladder-intact DFS will be defined as the time from the first study treatment to earliest evidence of progression to muscle-invasive disease in the bladder, regional pelvic progression, distant metastasis, bladder cancer–related death, or cystectomy. Data for patients without an event will be censored at the last date known to be alive and event-free. Data for patients who died from causes other than bladder cancer will be censored at the day of death.

- PFS, defined as the time from the first study treatment to the first occurrence of progression to muscle-invasive disease based on cystoscopy and urine cytology or death from any cause. Data for patients without a PFS event will be censored at the last date known to be alive and progression-free.
- Cystectomy-free survival, defined as from start of study treatment to bladder removal for any cause or death from any cause. Data for patients alive without cystectomy will be censored at the last date known to be alive without cystectomy.
- Overall survival, defined as the time from the first dose of study treatment to death from any cause. Data for patients who have not died will be censored at the last date known to be alive.

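### PFS in Section 6.4.2 ties progression to cystoscopy and urine cytology and leaves out pelvic and distant progression, so non-fatal metastasis and invasion first found at cystectomy are not events as written

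*Combined protocol and SAP*

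**What the plan says.** The outcome-measures section (3.5.4) reads "PFS, defined as the time from first study treatment to the first occurrence of progression to muscle-invasive disease or death from any cause", and the synopsis says the same. The analysis section (6.4.2) adds a method: "progression to muscle-invasive disease based on cystoscopy and urine cytology or death from any cause". Patients without an event are censored when last known to be alive without progression, and all progression calls are the investigator's.

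Other parts of the protocol use a wider notion of progression:

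- Section 4.6.2 lists among the reasons to stop treatment "Disease progression (e.g., muscle-invasive or metastatic UC".
- Section 4.5.5 states "Patients with evidence of disease progression to muscle-invasive or metastatic disease at any timepoint will be discontinued from study treatment".
- Bladder-intact DFS, defined just before PFS in Section 6.4.2, includes "regional pelvic progression, distant metastasis".

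On the two named methods, Section 3.1.2 says of cytology: "A positive cytology result only indicates presence of disease and cannot be used alone to determine disease progression". The cystoscopy criterion for complete response is read together with histology; one qualifying finding is "bladder appears abnormal but all biopsies are negative".

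**The concern.** Depth of invasion is established on tissue. Cystoscopy shows the surface of the bladder, and the protocol itself says that cytology alone cannot establish progression. A definition naming only these two methods does not fit the event it describes, and it is narrower than the endpoint stated in Section 3.5.4.

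The cystectomy case is foreseeable. Patients with high-grade disease at or after the 6-month biopsy stop treatment and are offered cystectomy or other options. No bladder remains to inspect after cystectomy, and although tissue is requested from the specimen, nothing links it to PFS.

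The omission of pelvic and distant spread means that PFS can describe as progression-free a patient who stopped treatment because of progression. The reported curve could then miss some of the most serious outcomes and disagree with other parts of the same report.

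**Working it through.** **1. Definitions side by side**

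| Place | Muscle invasion | Method named | Pelvic or distant spread | Death |
|---|---|---|---|---|
| PFS, synopsis and 3.5.4 | yes | none | not counted | any cause |
| PFS, 6.4.2 | yes | cystoscopy and cytology | not counted | any cause |
| Bladder-intact DFS, 6.4.2 | yes | none | both counted | bladder cancer only; other deaths censored |
| Treatment discontinuation, 4.5.5 and 4.6.2 | yes | none | metastatic named | n/a |

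**2. Three patients under Section 6.4.2 as written**

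- *Muscle invasion on biopsy or TURBT.* Histology is not named, but it is plausibly part of the cystoscopic work-up. Probably counted.
- *Muscle invasion first seen in the cystectomy specimen.* This is not a cystoscopy or cytology finding. Not counted on a literal reading.
- *Distant metastasis without muscle invasion, patient alive.* Not an event under any of the three definitions. Sections 3.1.2 and 4.5.11 specify continued tumor assessment only for patients who stopped for reasons other than recurrence, progression or cystectomy. A later bladder event could therefore be missed, leaving death as the main remaining route to an event.

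**3. Direction**

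Leaving out a non-fatal event can only delay or remove a PFS event. Estimated PFS is therefore the same or higher, never lower.

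**4. Size**

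The plan gives no PFS rate, event count or power, so there is no stated figure to reproduce. Without censoring, one uncounted event moves the PFS proportion by 1/N:

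- N=10: 1/10 = 10 points
- N=12: 1/12 = 8.3 points
- N=20: 1/20 = 5 points

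The number of such events has to be assumed. Two illustrations follow.

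*(a) Metastasis first.* Section 1.1.1 cites 45% progression to muscle invasion by year 5 in two very-high-risk groups. With an exponential model, λ = −ln(0.55)/60 = 0.00996 per month. Deaths are ignored. Let the metastasis-first hazard be a share s of λ (assumed).

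- Not counted: exp(−18λ) = 83.6% at 18 months.
- Counted, s = 5%: exp(−18 × 1.05λ) = 82.8%, a gap of 0.7 points before rounding.
- Counted, s = 30%: exp(−18 × 1.30λ) = 79.2%, a gap of 4.4 points.

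*(b) Invasion found at cystectomy.* Uncounted events = N × (1 − CR rate) × share having cystectomy × 0.30. The 0.30 comes from Section 1.1.2, where a background study "revealed a 30% incidence of upstaging following cystectomy". The CR rates of 40% and 50% at N=20 appear in Tables 11 and 12. The cystectomy share is assumed at 25% to 100% of non-responders.

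- CR 50%, share 25%: 20 × 0.50 × 0.25 × 0.30 = 0.75 events, or 3.8 points.
- CR 40%, share 100%: 20 × 0.60 × 1.00 × 0.30 = 3.6 events, or 18 points.

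Illustration (b) is upper-end, because it treats every upstaging as upstaging to muscle invasion.

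**The case against.** The best defence has four parts.

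*Histology is implied.* A reader might infer that Section 6.4.2 excludes all pathology. The documents do not support that. Section 6.4.1 describes the primary endpoint by cystoscopic assessment and cytology, yet Section 3.5.4 requires bladder biopsies for that same endpoint. Section 4.5.5 speaks of cystoscopy and TURBT assessments together, and the investigator judges progression. This stands for biopsy and TURBT. It does not reach a cystectomy specimen.

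*The narrow PFS is deliberate.* All three definitions name muscle invasion or death, Section 1.1.1 calls progression to muscle invasion the main worry, and a stopping rule need not define an endpoint. That is a fair point, but no reason for leaving out spread is given. The method clause in Section 6.4.2 is a mismatch either way.

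*Other endpoints show these patients.* Only in part. Cystectomy is itself an event in bladder-intact DFS and in cystectomy-free survival, so the stage found in the specimen is never separately visible. Bladder-intact DFS is also not a clean substitute: death from any cause is an event in Section 3.5.4, while Section 6.4.2 censors deaths from other causes.

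*Deaths count.* A fatal metastatic case is delayed rather than lost, provided that the death is captured. With the last visit expected about 120 weeks after the last enrollment, some deaths may fall outside observation.

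**Conclusion.** The point holds as a defect in an endpoint definition. Taken literally, Section 6.4.2 leaves two kinds of progression outside PFS: non-fatal pelvic or distant spread without muscle invasion, and muscle invasion first found at cystectomy. Only the direction of bias, towards longer PFS, follows from the text.

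A reader might go further and multiply the cited 30% by an expected number of cystectomies to put a figure on the overstatement. The documents do not support that step. The 30% is upstaging of any kind, not upstaging to muscle invasion. No cystectomy rate is given, and any total over a study of up to about 70 patients cannot be set against a single cohort of 10 to 12. The illustrations, from under 1 point to 18 points, depend on the assumed shares and are not estimates.

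The consequence is also limited by the role of PFS: it is a descriptive secondary endpoint, summarised by Kaplan-Meier, with no test, power or decision rule attached. The change is still worth making, because in cohorts this small a single event is visible in the estimate.

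**What to change.** In Section 6.4.2, delete the clause that bases progression on cystoscopy and urine cytology. Define the PFS event as the first of:

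- muscle-invasive disease confirmed histologically on any specimen (biopsy, TURBT or cystectomy);
- regional pelvic progression;
- distant metastasis;
- death from any cause.

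Date non-fatal events at the specimen or scan. Put the same definition in Section 3.5.4 and the synopsis.

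The cost is mainly wording, since bladder-intact DFS already requires pelvic and distant progression to be determined. One data item needs attention: cystectomy alone triggers the bladder-intact DFS event, so that endpoint does not need the stage in the specimen. The pathological stage from the cystectomy report must therefore be recorded where a cystectomy is done. PFS may look slightly less favourable as a result.

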Data for patients without the respective post-baseline assessment will be censored at the time of start of treatment plus one day. Time-to-event endpoints (duration of CR, bladder-intact DFS, PFS, cystectomy-free survival, and overall survival) will be summarized by cohort with use of the Kaplan-Meier method. Kaplan-Meier curves will be presented. Kaplan-Meier estimates of event rates at landmark timepoints (e.g., 6-, 12-, and 18-months) and median time to the event will be presented with the corresponding 95% CI. RFS rates and the corresponding 95% CI will be summarized at the 6-, 12-, and 18-month timepoints.

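### The Day-2 censoring rule in Section 6.4.2 is not limited to event-free patients, so read literally it discards early PFS and bladder-intact DFS events

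*Combined protocol and SAP*

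**What the plan says.** Section 6.4.2 defines each secondary endpoint with its own censoring sentence, then adds a general one: "Data for patients without the respective post-baseline assessment will be censored at the time of start of treatment plus one day". The next sentence lists the endpoints together: "Time-to-event endpoints (duration of CR, bladder-intact DFS, PFS, cystectomy-free survival, and overall survival) will be summarized by cohort with use of the Kaplan-Meier method".

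The endpoint-specific text reads as follows.

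- **PFS.** The event is the "first occurrence of progression to muscle-invasive disease based on cystoscopy and urine cytology or death from any cause". Censoring: "Data for patients without a PFS event will be censored at the last date known to be alive and progression-free".
- **Bladder-intact DFS.** Events include "regional pelvic progression, distant metastasis, bladder cancer–related death, or cystectomy. Data for patients without an event will be censored" at the last event-free date. One kind of death is handled separately: "Data for patients who died from causes other than bladder cancer will be censored at the day of death".
- **Cystectomy-free survival.** "Data for patients alive without cystectomy will be censored at the last date known to be alive without cystectomy".
- **Overall survival.** "Data for patients who have not died will be censored at the last date known to be alive".

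Apart from the separate sentence on other-cause deaths, each of these censoring sentences applies only to patients who have not had the event. The general sentence has no such limit. The plan does not say which rule prevails or what the respective assessment is for each endpoint.

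Two other places matter. Section 3.1.2 schedules cystoscopy and cytology every 12 weeks, and it and Appendix 3 put the first on-study cystoscopy at Week 10 in Cohorts 1B, 2 and 3. Section 6 keeps every treated patient in all analyses unless stated otherwise.

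**The concern.** A patient who fails before the first cystoscopy may have no post-baseline tumor assessment. For PFS and bladder-intact DFS, tumor assessment is the obvious meaning of the respective assessment. A programmer who follows the general sentence as it stands would censor that patient the day after treatment starts, although the endpoint definition counts the failure as an event.

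That censoring depends directly on outcome. The patient leaves the risk set on Day 2 and the failure never enters the estimate, so the curve can only move upward. Because all treated patients stay in the analysis set, the patient is still counted in the cohort while the event is lost. In cohorts of about 10 to 20, one such patient visibly changes a landmark estimate. If the point is left open, it will be settled at programming time, possibly with the data in view.

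**Working it through.** The plan attaches no figure to this rule, so there is nothing to reproduce. The check has two parts.

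**1. Which events are exposed.** For an event before the first cystoscopy with no post-baseline tumor assessment:

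| Endpoint and event | Section 6.4.2 endpoint definition | General sentence, read literally |
|---|---|---|
| PFS, death from any cause | Event on date of death | Censored Day 2: event lost |
| PFS, cystectomy | Not an event | No event to lose |
| Bladder-intact DFS, cystectomy or bladder cancer death | Event on its date | Censored Day 2: event lost |
| Bladder-intact DFS, other-cause death | Censored on day of death | Censored Day 2: date moves, no event lost |
| Cystectomy-free and overall survival | Event on its date | Unchanged if the respective assessment is cystectomy or vital status; lost only if it means tumor assessment |
| Duration of CR | Clock starts at first documented CR | Not reached this way, because a documented CR needs a post-baseline assessment |

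Section 3.5.4 words bladder-intact DFS differently and counts death from any cause. Under that wording, early other-cause deaths would be lost too. The difference between the two sections is a separate matter.

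**2. How much one event moves the estimate.** Cohort sizes come from Sections 3.1.1 and 6.1: about 12 in Cohort 1A, about 10 each in Cohorts 2 and 3, and 20 as the planned maximum for Cohort 2 or 3 in Table 12. The following are assumptions, not plan figures: *k* events at Week 6, *m* later events at Week 22, and no other censoring before 6 months.

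- Rule applied literally: the *k* patients leave on Day 2, so S(6 months) = (n − k − m)/(n − k).
- Early events counted: S(6 months) = [(n − k)/n] × [(n − k − m)/(n − k)] = (n − k − m)/n.

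| n | k | m | Literal rule | Events counted | Difference (points) |
|---|---|---|---|---|---|
| 10 | 1 | 0 | 100% | 9/10 = 90.0% | 10.0 |
| 12 | 1 | 0 | 100% | 11/12 = 91.7% | 8.3 |
| 20 | 1 | 0 | 100% | 19/20 = 95.0% | 5.0 |
| 10 | 1 | 2 | 7/9 = 77.8% | 7/10 = 70.0% | 7.8 |
| 12 | 1 | 2 | 9/11 = 81.8% | 9/12 = 75.0% | 6.8 |
| 20 | 1 | 2 | 17/19 = 89.5% | 17/20 = 85.0% | 4.5 |
| 12 | 2 | 2 | 8/10 = 80.0% | 8/12 = 66.7% | 13.3 |

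With no later events the difference is k/n. For one event that is 1/8 = 12.5 points at the Cohort 1B minimum of 8, and 1/28 = 3.6 points if Cohort 1B reached 18 and took all 10 expansion patients. In the no-later-event rows the literal rule also gives a Greenwood standard error of zero; with the event counted it is 8.0 points at n = 12.

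**The case against.** The strongest reply is that the general sentence is a fallback. It follows a list of rules that nearly all censor only event-free patients. PFS censoring needs a date when the patient was known to be progression-free, and an event-free patient never assessed after baseline has none. On that reading the sentence fills a gap and overrides no event definition. This is plausible and may well be the intent, but nothing in the text says so or sets an order of precedence.

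A reader might infer something stronger: that every death and cystectomy before the first cystoscopy becomes a Day-2 censoring, so that all the survival curves are inflated. The documents do not support that. The rule turns on the *respective* assessment. For overall and cystectomy-free survival the natural meaning is vital or cystectomy status, which a recorded death or cystectomy supplies. For the same reason, a patient known to be alive with the bladder in place at Week 9 need not be pulled back to Day 2 for cystectomy-free survival. Nor is the sentence an explicit instruction to censor events; it is an unresolved conflict.

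The exposed group may also be small. Section 4.5.5 allows unscheduled cystoscopy or cytology when progression or recurrence is suspected, and Appendices 1 and 2 include a tumor assessment at the treatment discontinuation visit. An early cystectomy with no post-baseline assessment is therefore less likely than the calendar alone suggests. Eligibility requires a life expectancy of at least 12 weeks and excludes muscle-invasive and metastatic disease. These points reduce the expected number of affected patients but do not settle the wording for the two exposed endpoints.

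**Conclusion.** The defect holds for PFS (early death) and for bladder-intact DFS (early cystectomy or bladder cancer death). For these the general sentence, read literally, contradicts the event definitions in its own section and biases the estimate upward. Overall and cystectomy-free survival are exposed only under the less natural reading of *respective*.

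The size is conditional, because the documents give no rate of death or cystectomy before the first cystoscopy. If one such event occurs in a cohort, the 6-month estimate is too high by about 8–10 points at n = 10–12 and 5 points at n = 20 with no later events. With two later events the figures are about 7–8 and 4.5 points. If none occurs, no event is lost. The affected endpoints are secondary and descriptive, and the primary 6-month CR rate does not depend on the rule. The change is still worth making, because it is cheap and settles the question before the data are seen.

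**What to change.** Rewrite the general sentence in Section 6.4.2 so that it:

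- applies only to patients with no event and no post-baseline tumor assessment;
- names the endpoints it covers, PFS and bladder-intact DFS, in place of the undefined *respective*;
- states that qualifying deaths and cystectomies before the first assessment count as events on their own dates;
- states that overall and cystectomy-free survival are censored at last known vital or cystectomy status, whatever the tumor assessment record;
- excludes duration of CR, since treatment start plus one day falls before that endpoint's time origin and its own censoring sentence already suffices.

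The cost is a short text change with matching programming, and no new data. The PFS and bladder-intact DFS estimates may come out slightly lower than under the literal rule.
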